6.6.4 Vibrotactile Threshold Testing

The measurement of cutaneous vibrotactile threshold is used to diagnose peripheral neuropathy. Cutaneous vibratory stimuli are carried on large myelinated sensory nerve fibers. These fibers are believed to be more sensitive to both diffuse and focal insult than are small myelinated and unmyelinated fibers carrying other sensory information such as pain or temperature. Thus, large fiber function abnormalities can be an early indicator of peripheral neurological disease in an individual at risk. Many occupational and environmental hazards, including heavy metals and organic solvents, can affect these fibers. Testing large fiber function may allow for early detection of neurotoxicity due to these and other agents.

The Vibratron II is a simple and widely used electromechanical vibrometer consisting of a controller unit and two identical transducer units that cause plastic posts protruding from their housings to vibrate at a frequency of 120 Hz. The intensity (amplitude) of the Vibration is controlled by the OUTPUT knob on the face of the controller unit. The amplitude is provided in "Vibration Units" on a digital display on the face of the controller. The Vibratron is a manually operated device and does not require computer interface for operation. It is relatively physically robust and readily portable. Data will be manually entered into the data system by the examiner. Set-up requires about 5 minutes. Each threshold requires about two minutes to obtain. We will obtain five threshold values (three descending and two ascending values) for each great toe, requiring a total of about 10 minutes. The vibration threshold for each toe is the median value obtained from values 2-5 (value 1 is discarded).

6.6.5 Standing Steadiness (Postural Stability)

The Advanced Mechanical Technology, Inc. (AMTI) force platform assesses postural stability by measuring the forces applied to the platform through the participant's feet. The device uses strain gauges in the metal platform and a computer interface to record the forces applied to it. The signals from these strain gauges are amplified, digitized, and stored in the computer. From these forces, a times series of locations of the participant's center of pressure can be collected. The path of these center of pressure locations is plotted on the computer screen and the length and velocity of the sway path over a standard time period (e.g., 60 seconds) is recorded. Other summary measures such as the average deviation in the lateral and anterior-posterior directions can also be calculated. We will repeat the test two times with the participant's eyes open and two times with eyes closed. A complete test session requires approximately 8 minutes.

6.6.6 Single Leg Stance

Measurement of postural stability allows for assessment of the integrated function of several components of the nervous system, including the vestibular apparatus, cerebellum, and proprioceptive system. Loss of functional integrity of any of these systems secondary to disease or toxic exposure may affect postural stability.

We will measure the single leg stance by asking the participant to stand on one leg and maintain balance for 30 seconds. If the participant is unable to maintain their balance for the entire 30 seconds, then the procedure will be repeated up to two additional times

6.6.7 Long Distance Corridor Walk (LDCW)

Insufficient cardiovascular fitness may be a major mechanism through which different behaviors and diseases contribute to functional decline; a key landmark on the pathway from independence to disability. As substantial decline in exercise tolerance may precede recognition of mobility-related difficulty, particularly in

sedentary individuals, low exercise tolerance may be an early indicator of impending functional limitation.

The LDCW, a walking-based test of exercise tolerance and fitness level, developed for use in the Health ABC study, was designed to minimize shortcomings associated with self-paced walking tests. [46] The participant is asked to walk four hundred meters at their normal pace and the time to accomplish this task is recorded. Four hundred meters is the approximate distance an average healthy older adult can cover in 6 minutes and is comparable to the reference distance (1/4 mile) of a commonly used self-report measure of mobility-related difficulty. [46] Participants are told that they will be timed but are advised to walk as quickly as they can, without running, at a pace they can maintain over the 400 meters. The LDCW will not be performed with participants whose systolic blood pressure is greater than or equal to 180, diastolic blood pressure greater than or equal to 110, heart rate less than or equal to 40 beats per minute, or heart rate greater than or equal to 120 beats per minute. Participants who report recent (within last three months) heart attack or myocardial infarction, angioplasty or stent placement, unstable angina or heart surgery will also be excluded from the LDCW. Further, participants are excluded if they are not comfortable walking long distances without assistive devices or if they are wearing shoes that make walking difficult.

6.6.8 Trail Making

The trail making test is a paper and pencil test that measures multiple domains, including visual search, scanning, speed of processing, mental flexibility and executive functions. The test consists of two tasks. In Task A, participants are asked to draw lines sequentially connecting 25 encircled numbers distributed on a sheet of paper. Task B is similar to task A, except the participant must alternate between numbers and letters (e.g., 1, A, 2, B, 3, C).

6.7 Neurobehavioral Examination

We will use the Behavioral Assessment and Research System (BARS) to measure neurobehavioral function. The purpose of the examination is to determine whether exposures to oil and oil dispersants are associated with brain or nervous system dysfunction. Individual components of the neurobehavioral exam are summarized in Table 2 and described in detail below.

We selected BARS for testing in this study because it was specifically designed for use in populations with limited levels of educational attainment and minimal experience using computers. The same design features that were implemented to improve ease of test administration – step-by-step spoken and written instructions, practice exercises, and a simple 9-button keyboard – have the added benefit of reducing staffing effort for examiners and variability in test administration. Our examiners will be trained and monitored by [name] and [name], collaborators at the University of Iowa who are experts in the field of neurobehavioral assessment and supported by the central study coordinator.

Table 2. Components of the Neurobehavioral Exam in Order of Presentation

Test	Function	Measurements
Finger Tapping	Response speed, coordination	
 • Number of taps completed in a fixed time
Symbol-Digit	Complex function/Information Processing Speed	
 • Latency to complete the matrices • Errors
Simple Reaction Time	Response speed	
 • Response latency or reaction time
Digit Span	Attention, memory	
 • Longest span forward and backward
Match-to-Sample	Visual memory	
 • Number correct • Correct response latency
Continuous Performance	Sustained attention	
 • Reaction time • Number of hits • Errors of omission • Errors of commission
Progressive Ratio	Motivation	
 • Number of ratios completed • Longest ratios completed

6.7.1 Finger Tapping

The tapping test measures response speed and coordination. The participant is instructed to tap as rapidly as possible with the right hand, the left hand and alternating hands over a 20 second period. Taps increase the height of a dark bar to suggest progress to the participant.

6.7.2 Symbol Digit

The symbol digit test, an assessment of complex scanning and visual tracking, is one of the most widely used and sensitive measures of neurotoxicity. The test presents nine symbols that are paired with a number between one and nine. The symbol-digit pairs are arranged in a 2 x 9 table at the top of the screen. A similar table at the bottom of the screen contains the symbols but not the digits. The participant is instructed to type the missing numbers that correspond with symbols in the bottom table as quickly as possible.

6.7.3 Simple Reaction Time

The simple reaction time test measures response speed. The participant is instructed to respond by pressing a response button as quickly as possible after seeing a stimulus on the screen or when a response button becomes backlighted. Fifty trials are presented and the latency for each button press is recorded.

6.7.4 Digit Span

The digit span test measures attention and memory. A series of numbers between one and nine is presented sequentially on the computer screen. The participant is instructed to reproduce the sequence of numbers by pressing the numbered response buttons in either the same or reverse order in which they were presented. The number of digits increases, starting from three numbers, until a failure criterion is met.

6.7.5 Match to Sample

The match to sample test measures visual memory. A 10 × 10 matrix of blocks is followed by three choices, among which one is the same as the sample stimulus. Participants are asked to select the sample stimulus.

6.7.6 Continuous Performance

The continuous performance test measures sustained visual attention. A series of stimuli are presented one at a time and in an unpredictable order for approximately 5 minutes. Participants are instructed to press a response button as quickly as possible after a cue-target (plus sign followed by a circle) is presented. Three hundred stimuli are presented; 20% of them are target stimuli.

6.7.7 Progressive Ratio

The progressive ratio test measures motivation. Participants are instructed to press a button multiple times and receive a “reinforcer” (smiley face) for completing the task. The criterion for earning a reinforcer increases with each successive trial. The total number of button presses or taps in two minutes is recorded.

6.8 Fractional Exhaled Nitric Oxide (FeNO)

eNO will be measured according to ATS/ERS standards, using a Sievers analyser (NOA-2080i) with chemoluminescent sensor. Clinical staff will conduct measurements with the participant in a seated position. The participant will place the mouth piece in their mouth, inhale for two to three seconds to total lung capacity, then exhale immediately at a constant flow rate (50mL/s) for ten seconds. The participant will be allowed to perform up to 8 maneuvers in order to achieve two measurements that agree within 5%. If the participant cannot perform two reproducible 10-second maneuvers, two 6-second maneuvers will be considered acceptable. FeNO will be collected immediately *prior* to the pulmonary function testing

6.9 Pulmonary Function Testing (PFT)

Pre and post-bronchodilator pulmonary function testing (PFT) will be conducted according to ATS/ERS guidelines [48]. Bronchodilation will be achieved through the administration of 4 metered doses of albuterol (90 µg per actuation, 4 puffs) through a spacer, with 30 seconds between puffs. Post-bronchodilator spirometry will take place 10-15 minutes after bronchodilator administration.

PFT will be performed using a portable, ultrasound transit-time based spirometer (EasyOn; NDD Medical Technologies, Chelmsford MA, USA, or a comparable model). A full Forced Vital Capacity maneuver will be conducted. We will obtain three ATS acceptable forced expiratory maneuvers out of a maximum of eight attempts before and after bronchodilator administration. Spirometry will be conducted with the participant seated and wearing a disposable nose clip. We will use new individually packaged, disposable mouthpieces for each subject and a new spacer for each subject. All spirometers will undergo standard quality control checks each day they are used.

To the extent possible, we will ask participants to not use their asthma inhalers on the day of the examination. We will record the timing and dosage of all asthma medications over the preceding seven days.

Participants who answer yes to any of the following questions will not undergo spirometry during the visit:

- In the past three months, have you had any surgery to your chest or abdomen?
- In the past three months, have you had a heart attack or stroke?
- In the past three months, have you had a detached retina or have you had eye surgery?
- In the past three months, have you been hospitalized for any other heart problem?
- Are you pregnant?
- Are you currently taking medication for tuberculosis?

In addition, participants with a blood pressure > 180 mmHg systolic or > 110 mmHg diastolic, or with a heart rate > 120 or < 40 beats per minute will not be tested.

Our exclusion questions include those used in BOLD [49] and PLATINO [50], multinational studies that enrolled over 14,000 adults over age 40 years for pre and post bronchodilator spirometry with only trained technicians. No adverse events occurred in either the BOLD or PLATINO studies. These exclusions are considered very conservative and these questions are not generally asked before spirometry is done in clinical practice.

Study staff conducting PFT will be required to take a web-based, NIOSH-approved spirometry course prior and to attend an in-person training session. Following training, staff will be required to submit 10 practice tests that are judged as acceptable by a PFT expert in order to receive certification of proficiency. During the run-in phase, our PFT expert will review PFTs on a weekly basis and will send findings to clinical site directors, along with suggested corrective actions. Clinical site directors or another

staff member experienced in PFT will work with study staff to improve performance. If necessary, additional training and practice sessions will be provided by the coordinating center in conjunction with the study PFT expert consultant. All tests will be over-read by a PFT quality control expert. We will re-train staff and continue to over-read all tests until 90% of scores meet quality standard and stabilize at that level of quality.

6.10 Mental Health Assessment

The clinical exam will include a more comprehensive assessment of mental health status, mental health needs, and resiliency than the telephone interview. This assessment allows for a more focused examination of complex interactions between mental and physical health status and will also cover domains that cannot be well-covered in a telephone interview, such as suicidal ideation and substance abuse. The assessment will repeat certain measures included in the telephone interview and will obtain information on participants' access and utilization of local mental health services. Participants will be administered the Patient Health Questionnaire-9 (PHQ-9), which measures current depressive symptoms, with an emphasis on depressed mood, the Primary Care PTSD Screen (PC-PTSD), a four item screener designed for use in medical settings, and the Positive and Negative Affect Scale-Short Form, (PANAS-SF) which, as its name suggests, measures levels of both positive and negative affect. We will also administer instruments based on the Generalized Anxiety Disorder 7-item (GAD-7) scale, the Connor-Davidson Resiliency Scale, the Traumatic Life Events Questionnaire, and the Financial Events Scale, which have previously been used in studies of the general population. This mental health assessment will be conducted near the end of the clinical exam.

Staff may encounter study participants during the clinic visit who are experiencing mild to severe psychosocial distress and will be trained to remain neutral when asking questions or responding to issues related to mental health conditions and to reply with sensitivity. In most situations, mild distress can be effectively addressed with an empathetic and respectful listening, allowing study activities to continue as planned. While the purpose of the exam is not to provide mental health diagnosis, counseling or care, every attempt will be made to connect participants in need with mental health services available in their community (lists of such services have been compiled (and will be updated as needed) with the assistance of other State and Federal Agencies and has been actively used throughout the Gulf STUDY.

Mental health referrals will be based on responses to the PHQ-9, the PC-PTSD, and the GAD-7. We will use validated cutoff points to systematically assess mental health distress and provide real-time referrals. Follow-up calls will be placed to all participants who receive a mental health referral to available mental health services in their area to determine if services were obtained and to provide additional information regarding health services, if necessary.

Staff will also be trained to respond to more serious signs of mental health distress, such as suicidal or homicidal thoughts, that require additional interventions. Participants who express such thoughts will be assessed for signs of acute distress and asked if they have plans, intentions, and means to act on their thoughts. Based on

these assessment findings, study staff will take appropriate action, as summarized in Table 3 below.

Table 3. Action Plan for Responding to Suicidal and Homicidal Thoughts

Individual at Risk	Imminent Danger*	Action
Self	No	
 Continue study activities, depending on level of emotional distress Offer a mental health care referral and follow-up call for all referrals
Self	Yes	
 End study activities Refer to emergency care at local community services if available, or through national Hotline Escalate to study managers and investigators Follow-up call for all referrals
Other	No	
 Continue study activities, depending on level of emotional distress Offer a health care referral and follow-up call for all referrals
Other	Yes	
 End study activities Call 911 Escalate to study managers and investigators Follow-up call for all referrals

* Homicidal or suicidal thoughts combined with plans, intention, or means to act on thoughts.

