8.1.5 Mandatory Reporting Requirements

In addition to personal safety training, the HVAs will be trained to detect signs of turmoil and abuse in the homes. Should a HVA witness signs of child, spouse or elder abuse while in the participant’s home, the HVA will immediately generate an incident report and transmit this to their Regional Manager and to the Coordinating Center. The Coordinating Center will immediately contact the NIEHS Project Officer and after appropriate consultation will report the situation to local authorities in accordance with applicable laws.

8.1.6 Identifying and Dealing with Mental Health Issues, Domestic Violence, and Acute Physical Illness

Study staff may encounter participants who are experiencing mental health issues, domestic violence, or acute physical illness when they interact with participants over the phone (i.e. on the study hotline or during telephone interviews) or during home visits. Staff will be trained to handle these situations according to standardized procedures that are adapted from approaches developed by the CDC and SAMSHA. In brief, the general approach involves study staff assessing the level of risk and taking appropriate action to prevent harm to the participant or others.

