8.1.6.1 Mental Health Issues

Due to the economic, social and potential health impacts of the oil spill, staff may encounter potential recruits and study participants who are experiencing mild to severe psychosocial distress. Call center and field staff will be trained to remain neutral when asking questions or responding to issues related to physical or mental health conditions

and socioeconomic status and to reply with sensitivity. In most situations, mild distresses can be effectively addressed with an empathetic and respectful listening, allowing study activities to continue as planned. When these approaches fail, study staff will offer to provide health care referrals and to continue study activities at a later date. Staff will also be trained to respond to more serious signs of mental health distress, such as suicidal or homicidal thoughts, that require additional interventions. Those who express such thoughts will be assessed for signs of acute distress and asked if they have plans, intentions, and means to act on their thoughts. Based on these assessment findings, study staff will take appropriate action, as summarized in Table 5 below.

Table 5. Action Plan for Responding to Suicidal and Homicidal Thoughts

Individual at Risk	Imminent Danger*	Action
Self	No	
 • Continue study activities, depending on level of emotional distress • Offer a health care referral • Offer to “hotlink” to National Suicide Prevention Hotline
Self	Yes	
 • End study activities • Offer to “hotlink” to National Suicide Prevention Hotline • Call 911, if referral to hotline is declined • Escalate to study managers and investigators
Other	No	
 • Continue study activities, depending on level of emotional distress • Offer a health care referral
Other	Yes	
 • End study activities • Call 911 • Escalate to study managers and investigators

* Homicidal or suicidal thoughts combined with plans, intention, or means to act on thoughts.

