8.1.6.4 Escalation and Documentation

Study supervisors and managers will be immediately notified of all cases involving active suicidal or homicidal thoughts (i.e. thoughts combined with intentions, plans, or means), domestic violence situations, and acute medical emergencies. Upon notification, study managers will notify study investigators and seek advice for any cases that fall outside the standardized response procedures. Study staff will be responsible for completing incident reports to document these situations.

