Approximately 6,500 cohort members from Louisiana, Mississippi, Alabama, and Florida will be invited to take part in the clinical examinations. We will invite all cohort members who were previously identified as a potential participant in the ***Biomedical Surveillance Sub-cohort*** during the baseline phase of the study (and for whom additional baseline laboratory tests were performed) to participate in a clinic visit, provided they live within 60 miles of a study clinic. We will augment this sample with additional cohort members who live within driving distance of one of two clinics in New Orleans, Louisiana and Mobile, Alabama. The clinical examinations will be performed in controlled clinical settings under the direction of health professionals from the University of South Alabama (USA) and Louisiana State University (LSU) Health Sciences Center. The clinic exams and procedures are described below, but briefly these research exams will include anthropometric measurements, biological sample collection, neurobehavioral evaluations, pulmonary function testing, and mental health questionnaires. The exams are for research purposes only and are not intended as delivery of primary or specialty health care services. Referral networks such as those developed for Phase 1 of the GuLF STUDY will be developed/ augmented to help those participants who wish to pursue clinical follow-up find appropriate services. The exam is expected to take between 3.75 and 4.0 hours and participants will be compensated for their time and travel costs as described below.

Study Oversight

The Principal Investigator will monitor and evaluate progress of the study, including periodic assessment of accrual, administration of informed consent, data quality and

timeliness of data collection, participant risk versus benefit, performance of contractors and other factors that can affect study outcome. This monitoring will also consider factors external to the study, such as scientific findings that may have an impact on the safety of the participants or the ethics of the study.

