There may be some minor discomfort associated with blood collection, including temporary pain, bruising, or swelling at the phlebotomy site. Fainting during blood collection is exceedingly rare.

13 Adverse Event Reporting

Adverse events that are related to clinical procedures and that require clinical intervention are expected to be very uncommon and occur in less than 1% of the study population. Any clinically-significant, procedural-related adverse events requiring medical attention will be reported to the IRBs during the annual continuing review.

Study staff may encounter participants who report or display symptoms of acute, pre-existing medical or mental health conditions that are not related to participation in the study. The results of study procedures, such as blood pressure measurement, may indicate the need for immediate medical attention for poorly controlled or previously undiagnosed illness. Clinic personnel may also observe signs that suggest the existence of reportable social or abusive behaviors or encounter participants who are experiencing mental health distress, suicidal ideation, or homicidal thoughts. Any pre-existing health problem, mental health distress, or social situation that requires a call to 911, local authorities, or social services will also be reported to the NIEHS IRB and local site IRBs as

an adverse event at the time of continuing review. The report will include information on the outcome of the actions taken in response to the event.

A clinically significant adverse event related to study procedures will be reported as a serious adverse event if it is life threatening, causes persistent or significant disability, leads to death, or requires medical or surgical intervention to prevent one of these outcomes. The principal investigator will be responsible for reporting all clinically significant serious adverse events related to study procedures to the NIEHS and clinical site IRBs within 24 hours of receiving notification that an event occurred.

Unanticipated problems are defined as any incident, experience, or outcome that meets all of the following criteria:

- unexpected in terms of nature, severity, or frequency given (a) the research procedures that are in the protocol and informed consent and (b) the characteristics of the subject population being studied;
- related or possibly related to participation in the research;

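### The clinic action plan for imminent danger to self (Addendum 3, Table 3) has no emergency-services step if the participant declines referral, although the telephone and home-visit plan (Table 5) has one.

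*Protocol*

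**What the plan says.** The protocol contains two action plans for suicidal and homicidal thoughts. They share a title and a footnote: imminent danger means such thoughts together with a plan, an intention or the means to act.

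- **Main protocol, section 8.1.6.1, Table 5.** The introduction to section 8.1.6 describes encounters that arise "when they interact with participants over the phone (i.e. on the study hotline or during telephone interviews) or during home visits". For imminent danger to self, staff stop study activities, offer a direct link to the national suicide hotline, and then: "Call 911, if referral to hotline is declined". They also escalate to study managers and investigators.
- **Addendum 3, section 6.10, Table 3.** This covers the clinic examination. For imminent danger to self, staff stop study activities and then: "Refer to emergency care at local community services if available, or through national Hotline". They escalate and make a follow-up call. For imminent danger to others, the same table tells them to call 911.

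Section 6.10 says the clinic assessment "will also cover domains that cannot be well-covered in a telephone interview, such as suicidal ideation and substance abuse". Section 2 of Addendum 3 describes the setting: "The clinical examinations will be performed in controlled clinical settings under the direction of health professionals".

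**The concern.** The two plans respond to the same defined state. One says what to do when help is refused and the other does not. A clinic staff member who follows Table 3 as written will stop the visit, make the referral and notify managers. If the participant then says no, the table gives no instruction to bring in emergency services. A colleague on the telephone or in the participant's home does have that instruction.

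The gap falls in the setting where the question is asked most directly. Suicidal ideation is a deliberate part of the clinic assessment, and participants who express such thoughts are asked about plans, intentions and means. Few people are likely to be affected, but the possible harm to each is grave and irreversible. This is a participant-safety and consistency point with no bearing on endpoints, sample size or analysis.

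**Working it through.** The protocol gives no figure to reproduce for this point, so the check is a comparison of text.

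**Step 1: the four imminent-danger rows**

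| Row | Stop activities | First response | 911 step | Escalate | Follow-up call |
|---|---|---|---|---|---|
| Table 5, self | Yes | Hotline link offered | Yes, if declined | Yes | Not listed |
| Table 5, other | Yes | 911 | Yes | Yes | Not listed |
| Table 3, self | Yes | Emergency care if available locally, or hotline | **None** | Yes | Yes |
| Table 3, other | Yes | 911 | Yes | Yes | Yes |

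Escalation appears in 4 of 4 rows and a 911 step in 3 of 4. The exception is clinic danger-to-self.

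**Step 2: does anything else cover refusal at the clinic?**

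- *Emergency-care referral.* It depends on local availability and can otherwise become a hotline referral. A declined hotline referral is exactly what triggers 911 in Table 5.
- *Escalation.* It does not depend on the participant's agreement, so it is real protection. But the other three rows pair it with a 911 step, and section 8.1.6.4 adds notification on top of the Table 5 actions: "Study supervisors and managers will be immediately notified of all cases involving active suicidal or homicidal thoughts". In its other rows, then, the sponsor does not treat escalation as a replacement for 911.
- *Follow-up call.* Its stated purpose in section 6.10 is "to determine if services were obtained and to provide additional information regarding health services, if necessary". That is not an emergency response.
- *Table 5 itself.* Section 8.1.6 is framed around telephone contact and home visits, and Addendum 3 has its own table, so the Table 5 fallback does not by its terms reach the clinic.
- *Addendum 3, section 13.* It foresees 911 calls at the clinic, but as a rule for reporting to the review boards: "mental health distress, or social situation that requires a call to 911, local authorities, or social services will also be reported". It sets no trigger for making the call.

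None of these gives clinic staff an emergency-services step on refusal.

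**Step 3: how many people pass through this assessment?**

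Addendum 3, section 4, plans about 6,500 invitations and about 62% participation: 6,500 × 0.62 = 4,030, which agrees with the stated 4,000 or so completed exams. This is an upper bound for the mental health assessment, because Table 1 of Addendum 3 does not mark that component for the abbreviated exam. With *a* the share of abbreviated exams (not given in the protocol; values assumed here), the number assessed is 4,000 × (1 − *a*):

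- *a* = 0: 4,000
- *a* = 0.10: 3,600
- *a* = 0.20: 3,200

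These are people assessed, not people affected. The protocol gives no rate for imminent danger to self or for declined referrals.

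**The case against.** The best case for leaving Table 3 alone runs as follows.

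**The row already has an emergency step, and the difference may be deliberate.** It is the only one of the four rows that refers the participant to emergency care; Table 5 starts lower, with a hotline offer. Table 3 also rewrites both danger-to-self rows and adds follow-up calls throughout, which looks more like adaptation to a clinic run under health professionals than a dropped line. Different settings can properly have different plans. *What stands:* the gap is narrow, confined to refusal, and the clinic setting could justify a different response. But the addendum as shown names none, and the same setting did not remove the 911 call for danger to others from the same table.

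**Absence is not proven.** Table 3 is described as a summary. Staff are to be trained and certified using manuals and job aids that are not part of the document, and a short stretch of Addendum 3 before the training text is not in the copy reviewed. *What stands:* a rule could exist there, and this limits confidence. Table 5 is also a summary, however, and it includes the step.

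**Unusual cases can be handled through escalation.** Section 8.1.6.4 has managers notify investigators and seek advice on cases outside the standard procedures. *What stands:* if applied to the clinic, that would give a route to advice. It still would not tell the person in the room to call for help.

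**A fixed rule is broad.** Because the definition is met by thoughts plus means alone, a mandatory call on refusal would cover some people whom a clinician on site might manage otherwise. *What stands:* the breadth is real, but the sponsor already accepts it, with the same definition, for telephone and home-visit contacts.

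**Conclusion.** The point holds. Read as written, the clinic plan leaves a participant who has suicidal thoughts plus a plan, intention or means, and who declines referral, without any emergency-services step. The telephone and home-visit plan provides that step for the same defined state. Some protection remains at the clinic: the visit stops, emergency care or the hotline is recommended, managers and investigators are told, and a follow-up call is planned.

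The number affected is unknown and probably small, out of at most about 4,000 people assessed. The change is worth making because the outcome at stake is severe and the remedy is simple. Confidence is medium, since the conclusion assumes that neither the clinic manuals nor the unavailable text already supplies the missing instruction.

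**What to change.** In Addendum 3, Table 3, imminent danger to self, add the Table 5 step, widened to fit the clinic: staff call 911 if the participant declines the referral to emergency care or to the hotline. Keep the referral, escalation and follow-up call as they are, and bring the clinic manuals and staff training into line.

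The cost is one line in the table and a training update. The downside is an occasional extra 911 call, at a rate the protocol gives no basis for estimating.
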